#### Randomization and blinding

After collecting baseline data, the research nurse will randomly allocate patients into the intervention or control group. Block randomization (block size: 8, 10, or 12) will be used to ensure even participant distribution between the two groups. The block size and respective study group allocation sequence will be determined using a computer-generated sequence. Chronologically recruited patients will be allocated to the study groups by the nurse according to this computer-generated sequence. Participants allocated to the intervention group will receive the i-CARE intervention, while those allocated to the control group will continue to receive conventional care as arranged by the hospital. An independent research assistant who is blinded to study group allocations will collect post-intervention data.

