##### 1) Face-to-face orientation session

This single face-to-face session serves to orientate and prepare participants to actively engage in the upcoming internet-based intervention. The research nurse (RA1) will highlight the crucial role of patients themselves in managing the disease by assisting them to understand the links between their self-care behaviors and health consequences. A subsequent interactive skill-building session to ensure patients acquire the skills required for performing self-monitoring techniques, including blood pressure, heart rate and blood glucose measurement. The participants will be required to perform return demonstration to ensure skill acquisition. The nurse will then introduce the mobile application and assist the participants to register an account. Upon successful registration, a password will be provided. He/she will demonstrate the key functions of the application and assist the participant to personalize the setting according to their individualized risk profile and preferences. The nurse will emphasize the importance of compliance to self-care behaviors and will facilitate the participants to set self-directed goals at the end of this session.

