## **Outcome measures**

### *Primary outcome*

#### Self-care behaviors:

The Chinese version of Self-Care of Coronary Heart Disease Inventory (SC-CHDI) will be used to measure self-care behaviors. This self-reported SC-CHDI (22 items) measures self-care maintenance, self-care management and self-care confidence on a four-point response scale. Each subscale score is transformed to 100 points, with higher scores indicate better self-care for that attribute. It has acceptable reliability (Cronbach's alpha: 0.76 – 0.87), good factorial and convergent validity.

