## **Data collection procedure**

After obtaining the approval from the respective ethics research committees, the research nurse will recruit eligible participants from the cardiac clinics and wards of two regional hospitals in Hong Kong. The local PI will identify potential subjects from the admission record and follow-up list of the cardiac ward and clinics respectively, and refer them to the research nurse. The research nurse will screen their eligibility according to the predefined criteria. All the eligible patients will be invited to participate. He/she will introduce the study to potential participants verbally, supplemented with a written information sheet. After obtaining the participants'

written informed consent, the nurse will collect socio-demographic and clinical data through patient's self-report and medical record review, while the nurse will assist participants to complete the SC-CHDI, SAQ and MacNew through a secured online platform Qualtrics. The physiological, anthropometric and biomarkers will be collected according to the standard protocol. The research nurse will then allocate the participants into intervention or control group by block randomization, to receive the i-CARE intervention or usual care, respectively. The post-intervention data will be collected through the mobile application, a message will be popped up to remind the participants at 3 and 6 months thereafter. A trained research assistant who has no knowledge of the group allocation, will be responsible for collecting the post-intervention physiological, anthropometric and biomarkers. A subsample of the participants will be invited to participate in the qualitative phase. Semi-structured interviews will be conducted by the principal investigator with an interview guide, which includes open-ended questions to enquire about their engagement experience in the intervention.

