### **Data Analysis**

For the RCT study, data analysis will be performed according to the intention-to-treat principle. Baseline characteristics between the two study arms will be compared by t-test, chi-square or Fisher's exact test as appropriate. The generalized estimating equation (GEE) model will be used to compare the differential changes on the outcomes across the time points T0, T1 and T2 between the two study arms with adjustment for potential confounding variables. Baseline characteristics with p values < 0.25 for between-group difference will be considered as potential confounding variables. GEE model can account for intra-correlated repeated measures data and accommodate missing data caused by incomplete assessments or dropout, provided that the data are missed at random, and thus are particularly suitable for intention-to-treat analysis without the need of imputation for missing data. All statistical analyses will be performed using IBM SPSS 25.0. All statistical tests will be two-sided and a p-value < 0.05 will be considered statistically significant. For the qualitative study, the audio-taped data will be transcribed verbatim. The principal investigator will ensure accuracy of the transcription by cross-checking. Content analysis will be adopted to code the qualitative data on participants' perceptions and acceptability of the technology-based self-care support intervention. The analysis will also seek to understand why and how the study intervention influences patients' health behaviors. The codes will be organized into categories and subcategories, which will be analyzed for emerging themes. The trustworthiness of the qualitative analysis will be enhanced by audio-taping of the interviews, conducting an audit trail, involving two team members to code the qualitative data independently.

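### The three questionnaires move from nurse-assisted Qualtrics at T0 to the mobile application at follow-up; because that application is part of the i-CARE intervention, the effect of the switch could differ between arms

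*Combined protocol and SAP*

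**What the plan says.** Under Data collection procedure, before allocation and in both arms, "the nurse will assist participants to complete the SC-CHDI, SAQ and MacNew through a secured online platform Qualtrics". For follow-up, the same section says "The post-intervention data will be collected through the mobile application, a message will be popped up to remind the participants at 3 and 6 months". T1 and T2 are not defined in so many words; I take them as these 3- and 6-month points. The blinded assistant appears in that section for one task only: this person "will be responsible for collecting the post-intervention physiological, anthropometric and biomarkers".

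Randomization and blinding is wider: "An independent research assistant who is blinded to study group allocations will collect post-intervention data". It does not limit this to physical measures and does not mention the application.

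The primary outcome is self-report: "This self-reported SC-CHDI (22 items) measures self-care maintenance, self-care management and self-care confidence on a four-point response scale". SAQ and MacNew, both secondary, are also questionnaires.

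Access to the application is described only in the orientation session of the intervention arm: "The nurse will then introduce the mobile application and assist the participants to register an account". The usual-care section mentions no application access, and no follow-up questionnaire route is given for controls.

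Under Data Analysis, GEE is used to "compare the differential changes on the outcomes across the time points T0, T1 and T2 between the two study arms". Neither that section nor any other mentions mode of administration or equivalence of the two platforms.

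**The concern.** Platform and, apparently, level of help both change between the baseline and follow-up scores that the analysis compares. Someone helped by a nurse may answer self-report items differently, and leave fewer blank, than someone answering alone on a phone. A change from T0 then contains the change of mode as well as any real change in self-care.

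No model term can separate the two afterwards. On the written procedure every T0 score comes from one mode and every later score from the other, so mode coincides with the T0-versus-later contrast.

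Three things are at stake, in rising order of importance:

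- Within-arm change could show a false rise or fall.
- Person-to-person variation in the shift adds noise to individual changes. These feed the between-arm comparison and also the choice of the 30 interviewees, who are picked by low, medium or high change in the primary outcome (Study participants).
- If the shift differs by arm, the treatment effect on the primary outcome is biased. The follow-up platform is itself a main component of the intervention. By T1, i-CARE participants will have had nurse training and a 12-week programme on it; controls will be new to it or will use a route that the plan does not describe.

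**Working it through.** **Inputs from the documents (Study participants).** Effect size d = 0.4 (outcome SD taken as 1), two-sided 5%, 80% power, 100 per arm, 25% dropout, 268 in total. The calculation is for a comparison of arms at the post-intervention time point and uses no baseline correlation.

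**Inputs assumed.** T0-to-follow-up correlation rho = 0.5-0.6; person-to-person SD of the mode shift s = 0.25 or 0.5 outcome SDs; difference between arms in mean shift m = 0.1 or 0.2 SD. The documents give none of these.

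**1. The plan's own figure.** A two-sample t-test at d = 0.4 needs 99.08, so 100 per arm; power at 100 is 80.4%. With dropout, 100 / 0.75 = 133.3, so 134 per arm and 268 in total. The stated sample size reproduces.

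**2. A shift common to both arms.** If c is the common shift and d the true effect, mean change is c in controls (no true change) and c + d in the intervention arm. The difference is (c + d) - c = d. A simulation with c = 0.3, d = 0.4 and rho = 0.5 gave changes of 0.30 and 0.70 and a difference of 0.40, with the standard error unchanged at about 0.14. Within-arm change is wrong by c; the between-arm contrast is not.

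**3. A shift that varies between people.** The variance of an individual change is 2(1 - rho) + s². Power of a t-test on change, 100 per arm, d = 0.4:

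| rho | s | variance | d / SD | power |
|---|---|---|---|---|
| 0.5 | 0 | 1.0000 | 0.400 | 80.4% |
| 0.5 | 0.25 | 1.0625 | 0.388 | 78.0% |
| 0.5 | 0.5 | 1.2500 | 0.358 | 71.1% |
| 0.6 | 0 | 0.8000 | 0.447 | 88.2% |
| 0.6 | 0.25 | 0.8625 | 0.431 | 85.8% |
| 0.6 | 0.5 | 1.0500 | 0.390 | 78.4% |

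The loss is 2.4 points at s = 0.25 and 9.3 to 9.8 points at s = 0.5. A baseline-adjusted analysis, with variance 1 + s² - rho², falls from 90.1% to 80.4% (rho 0.5) or from 94.0% to 84.7% (rho 0.6) at s = 0.5.

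**4. Selection of interviewees.** If the three change categories are taken as tertiles (an assumption), simulation with the same rho and s moves about 14-16% of participants to a different tertile at s = 0.25 and 26-29% at s = 0.5.

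**5. A shift that differs by arm.** The bias in the contrast is m. Relative to the design effect, 0.1 / 0.4 = 25% and 0.2 / 0.4 = 50%. With no true effect, 100 per arm and SD 1, the standard error is sqrt(2/100) = 0.141:

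- m = 0.1: m / SE = 0.707. P(Z > 1.253) + P(Z < -2.667) = 0.105 + 0.004 = 10.9%.
- m = 0.2: m / SE = 1.414. P(Z > 0.546) + P(Z < -3.374) = 0.293 + 0.0004 = 29.3%.

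The sign is unknown. If the differential runs against i-CARE and the true effect is 0.4, the apparent effect is 0.3 or 0.2, and power falls from about 80% to about 56% or 29%.

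**The case against.** A reader might infer that the switch by itself biases the treatment effect. The documents do not support that: T0 is collected in the same way in both arms before allocation, the planned comparison is of change between arms, and a common shift cancels (step 2). Nor does a change of mode by itself cost precision. Precision suffers only if the shift varies between people, and at s = 0.25 the loss is small. A loss of 9-10 points needs mode to add variance equal to 25% of the outcome variance, for which the documents give no support. A common shift also leaves participants' ranking by change intact, so it does not disturb interviewee selection. All of this stands.

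A reader might also take it as settled that participants complete the questionnaires alone at follow-up. That is an inference from the application and the pop-up reminder. The randomisation section leaves room for the blinded assistant to collect them, so assisted completion is not excluded. This stands too, and it means that the mode of the primary outcome at follow-up is not fixed by the plan.

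Finally, the differential shift is assumed, and the documents do not say that controls will be refused the application. The plan cannot be said to contain a biased contrast. What remains is that it leaves open a route to one on a self-reported primary outcome: the follow-up instrument sits inside the intervention, and preparation to use it is described for one arm only.

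**Conclusion.** The point holds in a limited form. The change of platform is explicit; the loss of assistance is probable but inferred, and the two sections on follow-up collection must be reconciled. The effect on the planned contrast is nil for a common shift and, for a shift that varies between people, modest at s = 0.25 but material at s = 0.5. The main exposure is a differential shift, with the bias and false-positive rates in step 5. Those figures show sensitivity at 100 per arm under assumed values and do not estimate what will happen. The stated sample size is unaffected. The change is worth making before recruitment because mode cannot be separated from time in the analysis afterwards.

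**What to change.** In Data collection procedure, state that both arms complete SC-CHDI, SAQ and MacNew at T1 and T2 on the same Qualtrics form as at T0, outside the i-CARE application, at the contact where the blinded assistant takes the physical measures. Set one scripted, limited level of help for all three time points: participants enter their own answers, the helper only clarifies how to use the form, and participants are asked not to mention the application. Use messages to either arm only as reminders. Align the sentence on follow-up collection in Randomization and blinding with this text, and define T1 and T2 there or under Data Analysis.

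The cost is wording, a short script and a longer contact at T1 and T2. No new staff are needed, and no new visits, because the assistant already has to collect finger-stick lipids, blood pressure and waist-to-height ratio. The downside is a small added risk that a participant reveals the allocation to the assistant; self-entry and the request not to mention the application limit it.

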Given the robust evidence indicating the benefits of consistent self-care for CAD patients, there is a desperate need to identify effective and feasible interventions to optimize the care of this burgeoning population. With increasing evidence suggesting the beneficial effects of internet- and smartphone-based interventions on promoting self-care in CAD patients, it is timely to reduce the current evidence-practice gaps of suboptimal secondary prevention in this clinical cohort, particularly those not eligible for routine cardiac rehabilitation. This first-ever local study plans to develop a theory-guided, internet-based self-care support intervention in the format of a mobile application, entitled “internet-based CArdiac Rehabilitation Enhancement (i-CARE)”, for promoting self-care of patients with CAD. The intervention will eschew the traditional one-size-fits-all approach, instead, it will address the individualized risk profiles and comprehensive needs of the CAD patients who are routinely excluded from traditional cardiac rehabilitation.

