### Study participants

Adults will be eligible to join the study if they are: 1) living in the community, 2) owning a smartphone with internet access, 3) communicable in Cantonese, 4) able to type in Chinese or English, and 5) with a confirmed diagnosis of CAD. Individuals will be excluded if they have: 1) enrolled to a structured center-based or home-based cardiac rehabilitation programme in the past year, 2) known psychiatric problems, 3) impaired cognitive functioning (i.e. Abbreviated Mental Test  $\leq 6$ ), and 4) terminal disease with life expectancy  $< 1$  year.

For the RCT, the sample size is determined on the basis of a systematic review that identified small to medium effect sizes (0.42–0.66) of information and communication technology-based cardiac rehabilitation on health behaviors among patients with CAD. This study will conservatively assume an effect size as 0.4. The power analysis software PASS 14 (NCSS, Kaysville, UT) estimated that a sample size of 100 subjects per study group would give the proposed two-arm randomized controlled trial 80% power at a two-sided 5% level of significance to detect an effect size of 0.4 on the primary outcome between the control and intervention groups at the post-intervention time point. After allowing for a potential dropout rate of up to 25%, 268 subjects (i.e. 134/group). For the qualitative phase, a criterion sampling of 30 participants who have received the i-CARE program will be invited to join on the basis of their post-intervention changes in the primary outcome, with 10 participants from each

category (low, medium and high percentile). Maximum variations in the participants' sociodemographic and clinical characteristics will also be considered in the sampling procedure to ensure a wider range of data.

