#### Intervention group: i-CARE

Participants in the intervention group will receive a 12-week i-CARE intervention, which will be designed to cover the core elements of CAD self-care: self-care maintenance, self-care monitoring and self-care management. The intervention will comprise: 1) a single individualized face-to-face session and 2) an internet-based intervention through a mobile application, which is developed by the investigation team of this project. Various behavior change techniques will be used to increase the self-efficacy of CAD patients in enacting self-care behaviors. The details of these two care components are described as follow.

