##### 2) Internet-based intervention via a mobile application

The mobile application will consist of three key user interfaces, including the self-monitoring dashboard, the interactive self-care modules and the chat room. A group of 12 CAD patients with diverse socio-demographic background will be invited to test the user interface. Their comments will be incorporated to optimize the design, content, layout and visual features before the application is formally launched for testing.

The self-monitoring dashboard is a personalized interface that allows participants to select relevant parameters for regular self-monitoring according to their own risk profile, which include blood pressure, heart rate, lipid profile and blood glucose. In addition, the physical activity levels of each participants will be monitored with a pedometer. The

number of steps will be synchronized to the dashboard regularly. All parameters will be self-measured and entered to the dashboard by the patients on a daily or weekly basis except lipid profile, which will be entered by the research nurse according to the results extracted from the Clinical Management System. The participants can customize the application features on receiving notifications and motivational messages. The input data will be presented in a graphical format to visually demonstrate the changes over time.

The interactive self-care modules will cover the following topics: 1) CAD, its symptom monitoring and management, 2) medication management, 3) personalized risk factor control (e.g. body weight reduction, smoking cessation, blood pressure control, glycemic control, lipid control, and insomnia), 4) healthy diet, 5) activity and exercise, and 6) stress management. The contents of this module are consistent with the recommendations of major international guidelines on CAD management. A variety of interactive features will be used to improve engagement, motivation and knowledge acquisition of the participants, including the use of audio-visual format with animations and illustrations, peers with successful self-care experience will also be invited to share the tips with the participants. The participants will be guided to establish an individualized action plan, which an exhaustive list of actions in categories will be presented for the participants to select those actions according to relevancy and preferences.

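### Follow-up questionnaires, including the primary outcome, appear to run through the i-CARE app, and no common questionnaire route for both arms is stated

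*Combined protocol and SAP*

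**What the plan says.** At baseline, before allocation, all participants complete the SC-CHDI, SAQ and MacNew on Qualtrics with the research nurse's help (Data collection procedure). For follow-up the same section changes the route: "The post-intervention data will be collected through the mobile application, a message will be popped up to remind the participants", at 3 and 6 months. The sentence names no instrument and no arm. The next sentence gives the blinded assistant the physiological, anthropometric and biomarker measures; questionnaires are not in that list.

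The section on randomization and blinding is broader: "An independent research assistant who is blinded to study group allocations will collect post-intervention data". It gives neither instrument nor mode.

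Only one app is described, and it is the treatment. The Background defines i-CARE as "a theory-guided, internet-based self-care support intervention in the format of a mobile application", and the intervention section lists as a component "an internet-based intervention through a mobile application, which is developed by the investigation team of this project". Accounts are set up in the intervention arm's orientation session: "The nurse will then introduce the mobile application and assist the participants to register an account". Its interfaces are the dashboard, the modules and the nurse chat room; no questionnaire-only version is mentioned. Controls receive usual care without structured rehabilitation (Control group: Usual care).

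**The concern.** The SC-CHDI is self-reported, so a fair between-arm comparison needs the same route, reminders and help in both arms. If follow-up questionnaires sit inside the treatment, two problems arise.

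- **Control arm.** With no stated access to the app, control questionnaires would either be missing or be collected by some other mode with other reminders. Arm and mode of measurement would then be confounded on the primary outcome.
- **i-CARE arm.** Response would depend on the participant still opening the app. The programme is time-limited ("Participants in the intervention group will receive a 12-week i-CARE intervention") and the later follow-up falls after it ends, yet continued access is not stated. Participants who disengage, and may benefit least, would be the likeliest not to answer. The Data Analysis section relies on GEE without imputation, on condition that data are missing at random. Response tied to treatment engagement strains that condition.

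These two pathways do not touch blood pressure, waist-to-height ratio, lipids or events taken from records. Self-reported events have no stated mode, so they cannot be ruled out.

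**Working it through.** **Which measures are left for the app.** The blinded assistant has the physical measures and biomarkers. Events and mortality have their own route, through record retrieval and self-report. What remains is SC-CHDI, SAQ and MacNew. This is an inference by elimination, but nothing else in the documents gives these instruments a follow-up mode.

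**The plan's own figure.** Inputs from Study participants: effect size 0.4, two-sided 5%, 80% power, 25% dropout. The normal formula gives n = 2(1.960 + 0.842)²/0.4² = 98.1, so 99 per group. The t-test version gives 99.08, so 100. Then 100/0.75 = 133.3, so 134 per group and 268 in total. The stated size reproduces.

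**Illustrations.** The documents give no response, mode-shift or non-use rates, so every rate below is assumed. The scenarios are alternatives and must not be added together. Power is for a two-sided t-test at one time point, a simplification of the planned GEE over T0 to T2.

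(a) *Control questionnaires partly missing, at random.* Noncentrality = 0.4/√(1/100 + 1/n_c), with 100 i-CARE responders and n_c control responders out of 134.

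| Control response | n_c | Noncentrality | Power |
|---|---|---|---|
| 75% (the planned dropout) | 100 | 2.83 | 80% |
| 50% | 67 | 2.53 | 71% |
| 25% | 34 | 2.01 | 52% |

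With no control responses there is no between-arm comparison.

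(b) *Different mode in one arm.* With no true effect, a shift of s SD and 100 per arm, noncentrality = s/√(2/100). For s = 0.10 it is 0.71 and the rejection rate is 11% instead of 5%. A true 0.40 would appear as 0.30 or 0.50, depending on the sign of the shift.

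(c) *Engagement-linked loss in the i-CARE arm, controls fully observed.* Let q be the share of non-users, r the share of benefit they keep and m the share of them missing. Fix the true effect over all randomised participants at 0.40 SD. The effect in users is u = 0.40/[(1−q) + rq], and the observed effect is u[(1−q) + rq(1−m)]/[(1−q) + q(1−m)].

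| q | r | m | Observed | Bias |
|---|---|---|---|---|
| 0.10 | 0.5 | 0.5 | 0.410 | 0.010 |
| 0.10 | 0.5 | 1 | 0.421 | 0.021 |
| 0.10 | 0 | 0.5 | 0.421 | 0.021 |
| 0.10 | 0 | 1 | 0.444 | 0.044 |
| 0.25 | 0.5 | 0.5 | 0.424 | 0.024 |
| 0.25 | 0.5 | 1 | 0.457 | 0.057 |
| 0.25 | 0 | 0.5 | 0.457 | 0.057 |
| 0.25 | 0 | 1 | 0.533 | 0.133 |

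Seven of the eight combinations lie between 0.01 and 0.06 SD. The 0.13 SD case needs a quarter of the arm to be non-users, with no benefit and all of them missing.

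**The case against.** The app sentence names no questionnaire and does not confine the blinded assistant to physical measures. The section on randomization and blinding states, without restriction and in the paragraph that allocates both arms, that a blinded assistant collects follow-up data. Every participant qualifies by "owning a smartphone with internet access", so an assessment-only login or the baseline Qualtrics forms could serve controls. If both arms used one, the mode and reminder differences would disappear.

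Part of this stands. A collector for controls is named, and a workable route is feasible. What is missing is a mode that applies to both arms, and the two sections disagree on the assistant's role. Feasibility does not fill that gap. Fidelity monitoring does track the logins of all participants, but as monitoring of the intervention; it gives controls no account.

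A reader might infer two stronger things. One is that controls will go unmeasured on the primary outcome. The documents show an unspecified route, not that outcome. The other is that controls will be given the app and so contaminated. The sections on randomization and on the control group keep controls on conventional care, so giving them the modules and nurse chat would breach the plan. Contamination is not an expected result of it.

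**Conclusion.** The concern holds, and it should be fixed before follow-up begins because it governs how the primary outcome is obtained. It rests on the natural reading that the app sentence covers the three questionnaires. On that reading the written procedure ties a self-reported primary outcome to access to, and use of, the treatment in one arm, and gives the other arm no matching route. A larger sample would not repair this.

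The size cannot be determined from the documents. Under the assumed rates, the loss ranges from none (control response at the planned 75%) to a serious loss of power, or a false-positive rate about twice nominal. Engagement-linked loss under the stated assumptions inflates the effect, while a mode difference can act either way, so the net direction of bias is unknown.

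**What to change.** Replace the app sentence in the Data collection procedure with:

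> At 3 and 6 months, participants in both arms will complete the SC-CHDI, SAQ and MacNew through the same Qualtrics forms used at baseline, with identical reminders on the same schedule sent outside the i-CARE application. Forms will be self-completed; any help will be given only by the research assistant blinded to allocation, not by the research nurse who delivers i-CARE, and participants will be asked not to reveal their allocation.

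Align the section on randomization and blinding with this, stating which measures the blinded assistant collects in both arms. Report questionnaire completion by arm and time point, because a common route removes the asymmetry between arms but not all engagement-linked non-response.

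Cost: wording changes in two sections, reuse of existing forms, and some staff time for reminders outside the app. Follow-up help would come from a different person than at baseline, but the same in both arms. No extra participants or measures are needed.
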